11.3.4. Discordant Analysis on the Results of Molecular versus Conventional Methods

The level of discordance between the molecular method and the conventional method will be assessed by calculating the global study positive percent agreement (PPA) and negative percent agreement (NPA) from the results of the cUTI tests. It is noted that evaluating and incorporating the conventional method's inherent performance characteristics is out of scope for this study; hence, the NPA/PPA metrics serve only as estimates into the sensitivity and specificity of the molecular method.

The PCR and the C&S results will be captured and summarized using the following matrix:

	C&		
PCR	Positive	Negative	Total
Positive	a	b	С
			(a+b)
Negative	С	d	D
			(c+d)
Total	A	В	Е
	(a+c)	(b+d)	(a+b+c+d)

where each value a, b, c and d is a total number of pair-results collected in the study. The NPA/PPA metrics are calculated as:

$$PPA = \frac{a}{A} \times 100\%$$

$$NPA = \frac{d}{B} \times 100\%$$

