2.2. Schedule of Assessments

The schedule of assessments table provides an overview of the protocol visits and procedures. The investigator may schedule visits (unscheduled visits) in addition to those listed on the schedule of assessments, in order to conduct evaluations or assessments required to protect the well-being of the subject.

Table 1. Schedule of Assessments

Assessments	Screening and Baseline V1 (Day 0)	Treatment ⁱ V2 (Day 0 to 5)	End-of-Study V3 (Day 28 ± 7)	Unscheduled Visit ⁱ UV
Informed Consent	X			
Eligibility Criteria	X	X		
Demographics ^a	X			
Medical history	X			
Vital signs ^b	X		X	X
Physical Examination	Х		X	X
Concomitant therapy	Х	X	X	X
Randomization	X			
Urine sample	Х		X	Х
collection				
Urine PCR	X		X	xe
Urine C&S	X		X	xe
cUTI treatment		$\mathbf{X}^{\mathbf{f}}$	X ^d	X
Adverse events ^c	X	X	X	X
Study conclusion			X	X

¹ Treatment visit (Visit 2) and/or unscheduled visits may be conducted virtually

UPH-STD-05-01 Version: 0

Effective Date: 06/23/2023 Page 12 of 44

^a Demographics include sex, age, date of birth

^b Vital signs include body temperature (°C), SBP (mmHg), DBP (mmHg), HR (bpm) and may be conducted by the Investigator at their discretion

^c AEs will be collected from the time of informed consent to EOS. Any ongoing AEs at EOS will be followed until resolution or stabilization

^d cUTI treatment may continue at EOS and after patient's study exit

^e Additional urine testing (PCR, C&S, or both) may be ordered at unscheduled visits at treating Investigator's discretion

^f cUTI treatment must initiate within 24 hours of receiving the test results (either PCR or C&S as per subject's assigned arm)

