4. STUDY OBJECTIVES AND ENDPOINTS

This investigation intends to verify the clinical utility of urine PCR testing by comparing the diagnostic and therapeutic values of molecular diagnostic methods to traditional urine C&S in management of cUTI in adults.

Table 2. Study Objectives and Endpoints

OBJECTIVES	ENDPOINTS		
Primary			
To evaluate patients' symptomatic responses following diagnosis and treatment based on the results of the molecular methods versus the those of conventional urine culture method	• Number (and percentage) of patients in each study arm with favorable clinical outcome* at the EOS visit *favorable clinical outcomes are defined as a clinical response of improvement and/or cure a Clinical improvement is defined as 1) Resolution of cUTI signs and symptoms present at baseline, 2) Development of no new cUTI symptoms and/or 3) Avoidance of parenteral antibiotic therapy, in or out of hospital, at any time after randomization b Clinical cure is resolution of all acute signs and symptoms of cUTI and improvement to such an extent that no further antimicrobial therapy (IV or oral) is required for the treatment of the cUTI		

UPH-STD-05-01 Version: 0

Effective Date: 06/23/2023 Page **14** of **44**

Advarra IRB Approved Version 0, Date: 12 May 2023 / Pro00071764

Secondary

- To determine the efficacy of antibiotic selection using molecular methods versus the conventional urine culture method
- To assess clinical utility of PCR results during the clinical-decision-making phase in patient care
- To compare the availability of the antimicrobial susceptibility information from molecular testing and conventional testing at the time of initial antimicrobial therapy
- To quantify the overall agreeability between the diagnostic results generated by PCR versus C&S

- Number (and percentage) of patients in each arm with microbiological eradication** of all baseline pathogens at the EOS visit
 - **microbiological eradication of all baseline pathogens is defined as an end of study quantitative urine culture that shows all uropathogens found at baseline are reduced to <10⁵ CFU/mL and all baseline pathogens are not detected by EOS urine PCR (Cq>33)
- Subjective measurement of Treating Investigator
 Satisfaction Score as evaluated by the questionnaire at EOS

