5. STUDY DESIGN

5.1. General Design

This is a multi-center, randomized, parallel-assignment, open-label, clinical utility study to evaluate urine PCR cUTI testing by comparing the diagnostic and therapeutic outcomes of molecular diagnostic methods to those of traditional urine C&S in management of cUTI in adults. At least six (6) sites will participate in this study. Approximately 120 eligible volunteers will be enrolled per site. The study is designed to be a 28-day study, which includes sample collection, sample test, treatment, and follow-up. Patients who meet all of the inclusion criteria and none of the exclusion criteria and sign an informed consent form will be enrolled in the study. During the visit, each enrolled patient will provide a urine sample (at least 8 mL) at V1 and V3; The collected urine specimens will be analyzed using both PCR and C&S methods at

UPH-STD-05-01 Version: 0

[figure not shown]
Effective Date: 06/23/2023 Page **15** of **44**

each timepoint. Upon eligibility confirmation by treating Investigator(s), patients will be randomized in a 1:1 ratio as follows:

- Diagnosis and treatment based on the results of the urine PCR
- Diagnosis and treatment based on the results of the urine C&S

Table 1. Schedule of Assessments summarizes the study procedures to be performed at each study visit. Individual study procedures are described in detail below (see section 8). It may be required to perform outlined procedures at unscheduled time points, if deemed clinically necessary by the Investigator(s). Additional evaluation/testing may be deemed necessary by the Investigator(s) for reasons related to subject safety.

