11.3.2. Primary and Secondary Endpoints

The primary endpoint is the number (and percentage) of patients in each study arm with FCl at the EOS visit; this term is defined as a *clinical response of improvement* and/or *clinical cure*:

Clinical response of improvement is defined as:

1) Resolution of cUTI signs and symptoms present at baseline, and/or

UPH-STD-05-01 Version: 0

Effective Date: 06/23/2023 Page **28** of **44**

- 2) Development of no new cUTI symptoms, and/or
- 3) Avoidance of parenteral antibiotic therapy, in or out of hospital, at any time after randomization

Clinical cure is the resolution of all acute signs and symptoms of cUTI and improvement to such an extent that no further antimicrobial therapy (IV or oral) is required for the treatment of the cUTI

The secondary endpoints include:

- Number (and percentage) of patients in each arm with *microbiological eradication* of all baseline pathogens at the EOS visit; *microbiological eradication* of all baseline pathogens is defined as an end of study quantitative urine culture shows all uropathogens found at baseline are reduced to <10⁵ CFU/mL and all baseline pathogens are not detected by EOS urine PCR (Cq>33)
- Subjective measurement of Treating Investigator Satisfaction Score as evaluated by the questionnaire at EOS
- Turnaround Time (TAT: as measured in hours) of molecular diagnostic procedures compared to conventional diagnostics (time from collection of samples to complete identification of organism(s) and availability of antibiotic sensitivity results)
- Overall agreeability between the diagnostic results generated by PCR versus C&S as assessed by discordant analysis

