Appendix II. Urine Sample Collection

- Early morning urine specimens ('first void specimen') are preferred, however routine or random samples are acceptable.
- Upon sample collection, immediately refrigerate the specimen and submit to the central laboratory within 24 hours of collection (maintain at 2-8 °C when transporting).
- If transportation to the central laboratory is expected to exceed 24 hours, whole cups of urine specimen must be frozen. However, for expedited PCR test processing, aliquot 1mL of urine into two* separate 1.5mL Non-Stick RNase-Free microfuge tubes labeled with patient information. Aliquoted tubes (for PCR testing) and the remaining urine specimen in the cup (for C&S testing) must be place in the freezer (< -20°C).

UPH-STD-05-01 Version: 0

Effective Date: 06/23/2023 Page **39** of **44**

*One tube is for immediate processing on the following work day and the other is a backup in case testing needs to be repeated.

Methods	Supplies	Instruction
Clean-	- Sterile 90 mL container	Patient instructions:
catch	- Towelette	Step 1. Wash and dry your hands thoroughly.
Midstream		Step 2. Remove the container lid and set it aside. Do not touch inner surfaces.
		Step 3. Cleanse your urogenital area ("lower parts") with the towelette provided.
		Women: Wipe from front to back between the folds of skin.
		Continue to hold the skin fold apart until the urine sample is
		collected
		Men: Wipe the tip of the penis (if un-circumcised, retract the foreskin).
		Continue to hold the foreskin back until the urine sample is collected
		Step 4. Pass a small amount of urine into the toilet bowl.
		Step 5. Urinate into the container until the container is 1/2 to 2/3 full
		Step 6. Finish urinating into the toilet bowl.
		Step 7. Replace the lid and tighten firmly.
		Step 8. Wash and dry your hands thoroughly.

Note: The collector must NOT combine urine collected from separate voids to create one specimen of sufficient volume, under any circumstances.

Appendix III. Device specification: pathogen targets and Cq ranges, antibiotics resistance genes and Cq ranges

Pathogen targets	Cq ranges for pathogen detection
 Candida albicans, glabrata, parapsilosis, tropicalis 	
Chlamydia trachomatis	Critically High : 10.000 – 21.000
Citrobacter freundii/braakii	High : 22.000 – 26.000
Citrobacter koseri	Medium : 27.000 – 28.000
Enterococcus faecium, faecalis	Low : 29.000 – 32.000
Escherichia coli	Negative : 40.000 – 33.000;
Gardnerella vaginalis	09.000 - 1.000

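### The single positive/negative agreement table credits PCR and culture with agreeing even when they share no organism, which overstates PPA, and it leaves the visit undefined

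*Combined protocol and SAP*

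**What the plan says.** One secondary objective is "To quantify the overall agreeability between the diagnostic results generated by PCR versus C&S", and the matching endpoint in section 11.3.2 is "Overall agreeability between the diagnostic results generated by PCR versus C&S as assessed by discordant analysis".

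Section 11.3.4 is the whole method. It calls for the "global study positive percent agreement (PPA) and negative percent agreement (NPA) from the results of the cUTI tests", taken from one 2x2 table with PCR positive/negative in the rows and C&S positive/negative in the columns, "where each value a, b, c and d is a total number of pair-results collected in the study". PPA is a/A and NPA is d/B, where A and B are the culture-positive and culture-negative totals. On their use, it says that "the NPA/PPA metrics serve only as estimates into the sensitivity and specificity of the molecular method". It gives no definition of a positive result, no organism match, no visit, no rule for several pairs from one patient and no confidence interval. Section 11.3.1 assigns this analysis to the ITT population.

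On the specimens, section 5.1 states that "each enrolled patient will provide a urine sample (at least 8 mL) at V1 and V3", with both methods run at each timepoint. A footnote to the schedule in section 2.2 adds that "Additional urine testing (PCR, C&S, or both) may be ordered at unscheduled visits". Section 9.1 gives the PCR panel 24 targets and has culture isolates identified to species.

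**The concern.** The two tests do more than call a specimen positive or negative. Each names organisms, and the organism bears on treatment: the sample PCR report in Appendix IV lists *E. coli* and *Gardnerella vaginalis* on separate lines with largely different candidate agents. A table that records only positive or negative cannot tell a pair that names the same organism from a pair that names different ones. Both land in cell a and both raise PPA.

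A PPA that is to be read as PCR sensitivity should not give PCR credit for a culture-positive specimen in which PCR missed the cultured organism and reported something else.

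The visit is a second gap. Baseline urine is taken before study treatment and V3 urine after it. If both enter one table, the result is a blend of two settings weighted by how many positive and negative cultures each happens to supply. Two analysts following section 11.3.4 could report different figures, and the choice could be made after seeing the data.

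**Working it through.** **Inputs.** The documents state no PPA, NPA, expected agreement or sample size for agreement, so there is no plan figure to reproduce. All rates below are assumptions. From the documents come the formulas PPA = a/(a + c) and NPA = d/(b + d), the enrolment ceiling of 720, and the 25% allowance for attrition and exclusion (section 11.1).

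**Step 1: does any-positive scoring follow from the text?** No sentence says so outright, but the pieces fit. The table has two categories per test. Section 8.3 treats the assigned result as UTI detected or not. In Appendix IV the sample negative PCR report is one that lists no organism, and the positive one is a list of those found. With no matching rule, a double-positive pair with different organisms has nowhere to go but cell a.

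**Step 2: effect of mismatch on PPA.** Let m be the share of double-positive pairs with no organism in common. Then

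matched PPA = a(1 − m)/(a + c) = PPA × (1 − m).

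Assume a = 300 and c = 30, so PPA = 300/330 = 90.9%.

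| m | Matched pairs | Matched PPA |
|---|---|---|
| 5% | 285 | 285/330 = 86.4% |
| 10% | 270 | 270/330 = 81.8% |
| 20% | 240 | 240/330 = 72.7% |

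NPA uses only b and d. The mismatched pairs are culture-positive, so NPA does not move.

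**Step 3: effect of visit, if all pairs are counted.** Scheduled pairs could number up to 720 + 720 = 1,440, or 720 + 540 = 1,260 if 25% have no V3 sample. Pooled PPA is the average of the visit values weighted by culture-positive pairs; pooled NPA is weighted by culture-negative pairs.

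One case in full: 720 pairs at each visit, culture positivity 40% at V1 and 5% at V3. Culture-positive pairs are 288 and 36; culture-negative pairs are 432 and 684.

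- NPA 50% at V1 and 75% at V3: (0.50 × 432 + 0.75 × 684)/1,116 = 729/1,116 = 65.3%.
- PPA 95% at V1 and 75% at V3: (0.95 × 288 + 0.75 × 36)/324 = 300.6/324 = 92.8%.

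Varying V1 positivity over 40–60%, V3 positivity over 5–15% and V3 pairs over 540–720:

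| Assumed V1 and V3 values | Pooled range |
|---|---|
| NPA 50% and 75% | 63–68% |
| NPA 50% and 30% | 36–40% |
| PPA 95% and 75% | 90–94% |
| Same value at both visits | Unchanged |

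So the visit matters only if agreement differs between visits, and the direction depends on how it differs.

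**The case against.** The best defence is that the endpoint is overall agreement, that a positive/negative table answers it, and that antibiotic selection and eradication have their own objective and endpoint. The endpoint is also descriptive, with no hypothesis or threshold, and section 11.3.6 leaves room for exploratory work. This stands as a limit on severity. It does not remove the gap, because section 11.3.4 offers PPA as an estimate of sensitivity and plans no organism-level table.

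It can also be said that the mismatch rates have no source, and that a pair with *Gardnerella* on PCR and *E. coli* on culture requires PCR to miss a panel organism at or above the culture limit of 10⁵ CFU/mL. The first part is right. On the second, mismatch need not involve a missed panel target: section 3 names *Enterobacter* among the common causes of UTI, and the Appendix III target list, as I read it, does not contain it.

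Three stronger readings are tempting, and the documents do not support them.

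- **That the plan pools V1 and V3 as a rule.** It does not say so. Section 8.3 describes concordance per patient on the result reviewed at Visit 2, which is the baseline sample, and sends discordant cases to section 11.3.4. The words about results collected in the study cover every visit if taken literally, so the visit is undefined.
- **That NPA is misstated.** Mismatch cannot change it. Targets such as "Chlamydia trachomatis" may put PCR-only detections in cell b and lower NPA, but a broader panel is a real difference between the tests and not a scoring error.
- **That repeated pairs make the planned standard error too small.** Section 11.3.4 plans no standard error, interval or test for PPA or NPA, so there is none to correct.

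**Conclusion.** The point holds in a limited form. Under section 11.3.4 as written, double-positive pairs with no common organism count as agreement, and PPA is overstated as an estimate of PCR sensitivity by the factor 1/(1 − m). In the illustration this is a drop from 90.9% to between 86.4% and 72.7% for m between 5% and 20%. The size rests wholly on the assumed m, which the trial data will show. The finding also rests on reading a positive result as any organism reported, which the sample reports and section 8.3 support but no sentence states.

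The visit is a matter of missing definition. Pooling would shift PPA and NPA only if agreement differs between visits, and a baseline-only table is a natural reading of section 8.3.

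The primary analysis is untouched. This is a cheap improvement to a descriptive secondary endpoint.

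**What to change.** Amend section 11.3.4 before the data are seen:

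1. Make the V1 pair, one per patient, the unit of the agreement table, and define a positive result for each test.
2. Keep the patient-level PPA and NPA. Add organism-matched PPA, in which agreement requires at least one shared organism, and per-organism PPA and NPA. Appendix III groups some species under one target, so state that a cultured species matches if it falls within a target that PCR reported.
3. Show V3 in a separate table. If a table with several pairs per patient is ever given an interval, use one that allows for clustering.
4. As a sensitivity table, restrict to PCR targets that the central laboratory's culture can report. The documents do not list these, so the laboratory must supply the list first.
5. State whether patients negative on both tests stay in cell d, since section 8.3 removes them from the study while section 11.3.1 analyses agreement in the ITT population.

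The cost is a few extra tables. Section 9.1 already has species identification recorded in the eCRF, and the eradication endpoint already follows baseline pathogens by both methods, so no new patients, samples or visits are needed. The reported PPA will be lower wherever mismatches occur, and the shared-organism rule is a choice that should be written down as such.

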11.3.5. Exploratory Investigations

Exploratory data analysis will be conducted by stratifying the data by various factors, that include but are not limited to the following:

- Study Sites (minimum 6 with n = 120)
- Age: Elderly (\geq 65yrs) versus Non-Elderly (\leq 65yrs)
- Gender: Male versus Female
- Comorbidities: High Risk (reporting comorbidities) versus Low Risk (no reported comorbidities)

UPH-STD-05-01 Version: 0

Effective Date: 06/23/2023

• Pregnancy: Pregnant (positive for test) versus Non-Pregnant (negative for test or not applicable)

11.3.6. Data Analysis of Secondary Endpoints

Descriptive and trend statistics will be performed for the secondary variables. Continuous variables will be presented with the average and standard deviation or median range, as appropriate, and categorical variables will be presented as proportions. An EDA will be performed for the secondary and exploratory variables (except safety) to analyze and investigate data sets and summarize their main characteristics, employing data visualization methods where applicable. Exploratory subgroup analysis will be based on the potential prognostic variables, including but not limited to the strata described in section 11.3.4. All statistical significance tests will be conducted with an alpha of 0.05, unless specified otherwise. If the underlying population is observed to deviate significantly from normality, a non-parametric statistical approach will be used.

12. PROTOCOL DEVIATION(S)

Protocol Deviation (PD) forms must be filed for an unintended or planned (if any and if approved in prior to occur) deviation from this protocol. PDs which place patients at increased risk of harm, or affect data integrity may be considered Protocol Violations (PVs) and must be reported to the appropriate regulatory authorities no later than 2 weeks (10 business days) from the time of identification. PDs will be filed in the applicable patient chart, and in the Trial Master File (TMF) upon study closeout. PDs will be filed and signed by delegated study staff and reviewed and signed by the Investigator. The Investigator will determine if the PD is reportable to the IRB based on an assessment of the patient's safety and/or the effects on the integrity of the study data.

13. PROTOCOL CHANGES

Any changes to the protocol must be tracked and documented in accordance with Good Documentation Practices, applicable SOPs, and regulatory oversight. The reasons for change must be documented in writing and provided to the regulatory bodies and approval must be granted prior to implementation unless subject safety is at risk. All versions of the protocol must be included in the TMF. All protocol changes will be documented in the study report.

14. ETHICAL CONSIDERATIONS

14.1. Ethical Conduct of the Study

UPH-STD-05-01 Version: 0

Effective Date: 06/23/2023 Page **31** of **44**

The study will be performed in accordance with ethical principles that are consistent with the ICH guidelines for Good Clinical Practice (ICF GCP E6(R2)), applicable regulatory requirements and the Sponsor's policy on Bioethics.

14.2. IRB Approval

All necessary forms, advertisements, and subject-facing study documents will be compiled into a submission to an Institutional Review Board (IRB) for approval prior to the conduct of the study. No conduct of the study will commence until written approval has been obtained from the IRB. The Sponsor and/or CRO must adhere to the requirements of the IRB and notify them of any study document changes, protocol amendments, and reportable protocol deviations/violations. Study termination must be reported to the IRB, and renewal of study approval must be obtained annually (or as per IRB's stipulations).

14.3. Informed Consent Form (ICF)

Informed consent will be obtained from patients by delegated study staff. The staff will explain the study and review each page of the consent document. Patients will then be given ample time to review the Informed Consent Form and ask any questions before signing the appropriate section(s). The Informed Consent Form (ICF) will contain pertinent study details, a statement indicating the patient is free to withdraw from the study at any point and for any reason, contact information of the IRB (to report ethical concerns), local and applicable regulations surrounding disclosure of personal and health information of the patients, and a section explaining the potential risk(s) of participating in the study. A copy of the informed consent document will be given to the patient for their records. The informed consent process will be documented in the source document (including the date), and the form signed, before the patient undergoes any study-specific procedures.

